Project Title: A Pilot Study Investigating the Post-Operative Analgesic Effect of NSS-2 BRIDGE device in

Subjects Undergoing Major Abdominal Oncologic Surgery: A Randomized, Double-Blind, Placebo

Controlled Trial

NCT03555266

Date: August 1, 2018

The purpose of this proposal is to request funds to support a pilot study investigating the use of a Percutaneous Auricular Nerve Field Stimulation device called the NFF-2 BRIDGE, which will be applied to sixty patients undergoing abdominal oncologic surgery with surgeon [name] at Shadyside Hospital. The data collected from this pilot trial will be used to supplement a future grant application to the NIH/NIDA to fund a large-scale randomized, placebo-controlled trial.

Statement of Problem

The current opioid epidemic has led to a renewed interest in exploring non-pharmacological techniques to treat post-operative pain. An increasing number of patients are suffering from the adverse effects of opioid use following surgery, including post-operative nausea and vomiting, respiratory depression, immunosuppression, constipation, and most recently, addiction. In the United States, over \$600 billion is spent every year on opioid addiction, including \$79 billion related to opioid addiction following surgery. Despite many initiatives to decrease the use of opiates in the preoperative setting, opioids continue to be regularly prescribed before, during and after surgery. Although the risk of opioid addiction following surgery is recognized, the percentage of patients becoming addicted to opioids following surgery is not well understood. To date, there has been virtually no agreement regarding the duration and dosage that qualify for opioid dependence following surgery, nor that a clear estimation of the factors such as biological, psychosocial and socioeconomic that increase the risk of using opioids for extended periods of time after surgery. Therefore, in order to combat this growing health crisis at the ground level, it is incumbent upon the medical community to explore alternative methods of pain control to treat the surgical population in order to reduce the incidence of post-operative opioid addiction.

Project Aims/Goals

Percutaneous Nerve Field Stimulation (PNFS) is one of these recognized methods that ongoing research has shown to be effective as a complementary method of pain management. While PNFS is not a novel concept, clinical indications of auricular field stimulation have been limited in the past due to requirement of bulky, stationary and non-disposable stimulators and electrodes. These technological limitations made it difficult to establish the real clinical potential of auricular stimulation for the perioperative management of pain in surgical patients, despite the demonstration that auriculotherapy has been shown to relieve pain in the postoperative setting.

The NSS-2 BRIDGE (Appendix 1) is a battery operated and disposable percutaneous auricular nerve field stimulator (Innovative Health Solutions, Versailles, IN, USA), that was recently cleared by the FDA and assigned a Class II Risk Designation; a class which includes surgical drapes, pumps and power wheelchairs. The indication for the NSS-2 BRIDGE is for the treatment of clinical symptoms related to opioid consumption and opioid withdrawal. These symptoms include abdominal pain, anxiety and post-operative nausea and vomiting; conditions which are also present following major oncologic abdominal surgery. The use of the NSS-2 BRIDGE device has been demonstrated to provide significant analgesia in patients with abdominal pain syndrome, and clinical trials are ongoing to assess the benefit of this approach for post-operative pain management. As compared to the present use of opioids for perioperative pain management, the use of a complementary, non-pharmacologic approach offers the advantage of analgesia without the associated side effects. **Mechanism of action of the Auricular**

Percutaneous Electrical Nerve Field

The NSS-2 BRIDGE devise allows for stimulation to branches of Cranial Nerves V, VII, IX and X, and the occipital nerves, identified by transillumination. Such a stimulation is transmitted to the central nervous and especially the limbic system, which is known to be a key component of the central nervous system response to stress, anxiety and the pain pathway. The nucleus involved by the stimulation include the amygdala (structure involved in the response to fear and anxiety), the thalamus (structure involved in the management of visceral and somatic pain, addiction), the nucleus of tractus solitarie (structure involved in the control blood pressure) etc.... The stimulation of these nucleus produces a decrease in the transmission of pain impulses from visceral and/or somatic structures to supraspinal areas, a reduction in anxiety and control of blood pressure and associated changes of the sympathetic and parasympathetic nervous system.

The Shadyside Foundation Grant will allow for the purchase of sixty NSS-2 BRIDGE devices (30 active, 30 placebo), and will support a research coordinator in the execution of a pilot study investigating the possible benefit of the device to supplement post-operative pain management. This pilot study will assess the possible benefit of using this non-invasive PNFS device as a way to reduce opioid consumption in patients undergoing abdominal debulking procedures with surgeon [name]. Preliminary data analysis has demonstrated that in the absence of the NSS-2 BRIDGE device, the average opioid consumption following major abdominal surgery using the current ERAS multimodal protocol is 100 mg IV morphine equivalent. It is expected that the use of the NSS-2 BRIDGE will be associated with a reduction of 50-70% opioid consumption following surgery. The primary endpoint for this pilot study will be overall opioid consumption and will constitute the basis of a National Institute of Drug Abuse (NIDA) proposal on opioid-free surgery. The expected timeline for this trial will be one year, from the start of enrollment to manuscript draft.

Specific Aims

1. This pilot study will prospectively investigate the efficacy of the NSS-2 BRIDGE device in reducing perioperative opioid consumption in opioid-naïve patients undergoing major abdominal surgery using the current SHY ERAS anesthesia protocol

4 of 12

2. To prospectively investigate the incidence of post-operative complications between the standard ERAS anesthesia protocol + active NSS-2 BRIDGE vs. ERAS anesthesia protocol + placebo (in-active) NSS-2 BRIDGE

3. To prospectively investigate role that the NSS-2 BRIDGE device may have in reducing opioid consumption after discharge and facilitating functional recovery

Study Design

The proposed pilot study will be conducted as a single-center prospective randomized double-blind, placebo-controlled trial at the University of Pittsburgh Medical Center (UPMC) Shadyside Hospital. Institutional review board approval will be obtained before eligible patients are recruited and consented. Trial will be registered at www.clinicaltrial.gov before beginning recruitment.

Recruitment

Potential subjects will be recruited in the pre-surgical clinic of [name] once they are scheduled for abdominal debulking surgery. Patients will be asked for their interest in pursuing a research study that involves wearing a percutaneous, auricular field stimulator for five days as a supplementary method of post-operative pain control. Patients who agree to participate in the trial will sign an IRB approved Informed Consent Form.

Randomization Process

Participating patients will be randomized by computer generated random numbers to either the control or intervention group.

Inclusion Criteria:

Over 18 years of age

Open abdominal debulking procedure as per our institution's Enhanced Recovery After Surgery (ERAS) anesthetic protocol.

Exclusion Criteria:

History of active depression, anxiety or catastrophizing

Active alcoholism or drug abuse

Severe chronic pain condition that requires daily preoperative opioid dependence

History of hemophilia

Patients with cardiac pacemakers

Patients with psoriasis vulgaris diagnosis

Treatment Groups

Control Arm: Control group will receive approved ERAS multimodal anesthesia protocol (Appendix 2) plus an inactive placebo NSS-2 BRIDGE device.

Interventional Arm: Intervention group will receive approved ERAS multimodal anesthesia protocol (Appendix 2) plus an active NSS-2 BRIDGE device

Data Collection and Outcome Measures

Once patient has signed the Informed Consent to participate in this pilot study, demographic information and medical history will be collected from each participant on the day of surgery. The NSS-2 BRIDGE device will be applied to the ear by trained researcher in the immediate post-operative setting (PACU), as the research team has completed the necessary training required by the company to apply the device. Rescue analgesia will be permitted as per the approved ERAS multi-modal anesthetic protocol (Appendix 2), however, the patient will be made aware at the time of consent and throughout the trial that they can drop out of the study at any time if they do not like wearing the NSS- 2 BRIDGE device.

The patient will be assessed 12, 24, 48, 72, 96 and 120 hours post-operatively to collect total opioid consumption, incidence of adverse events, and level of comfort while wearing the NSS-2 BRIDGE device. When the patient is discharged from the hospital, they will be asked to complete a patient satisfaction survey. For patients discharged with the device attached, removal instructions and pre-paid return envelope will be given to patient to remove the device at 120 hours and send back to the hospital. The patient will be contacted 3 months post-operatively to again assess patient satisfaction with the pain management after surgery, and to assess functional recovery.

Pre-and-Post Metric Evaluation

The use of a non-pharmacological NSS-2 BRIDGE has the possibility of providing analgesia to post-surgical patients and reducing the number of opioids required following abdominal surgery. This will significantly impact patient outcomes, as patients will experience fewer opioid-related side effects (such as respiratory depression, post-operative nausea and vomiting, constipation and delirium). This will also impact clinicians caring for post-operative patients, as there is the real potential they will have fewer conditions to monitor and treat as the patient recovers from surgery. The projected number of patients served by this project will initially be sixty enrolled participants at Shadyside Hospital, however, the data collected from this trial will serve countless patients and the community at large as physicians strive to move away from opioid use following surgery. Data collected from this pilot study will support a future proposal to the National Institute of Drug Abuse (NIDA) to fund a full-scale, randomized, placebo-controlled trial using the NSS-2 BRIDGE device.

Perhaps most importantly, the investigative use of the non-invasive NSS-2 BRIDGE device has the ability to significantly increase patient satisfaction in individuals who are opioid naïve or adverse to taking opioids as a method of pain control. Being able to offer the cancer patients at UPMC Shadyside such an alternative represents a great opportunity to increase patient satisfaction, outcomes and compliance as many patients increasingly fear the use of opioids. The NSS-2 BRIDGE will remain effective on the participant for five days, and will have lasting effects even after discharge from the hospital, which is a time when many patients turn to opioids to control pain. The way the efficacy of this device will be measured will be by comparing total perioperative opioid consumption between the intervention group (Standard of Care ERAS protocol + active NSS-2 BRIDGE) and control group (Standard of Care ERAS protocol + inactive NSS 2 BRIDGE), and total opioid consumption after discharge between the two groups. Other outcome measures include the incidence of respiratory depression, PONV, constipation and length of stay between the intervention and control groups.

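### The protocol promises a between-arm comparison of opioid use after discharge, but no opioid collection is described beyond 120 hours

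*Protocol*

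**What the plan says.** Three parts of the protocol bear on this.

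- **Aims.** Project Aims/Goals states that "The primary endpoint for this pilot study will be overall opioid consumption". Under Specific Aims, Aim 1 concerns the "efficacy of the NSS-2 BRIDGE device in reducing perioperative opioid consumption". Aim 3 concerns the device's role in "reducing opioid consumption after discharge and facilitating functional recovery".
- **Measures.** Pre-and-Post Metric Evaluation says efficacy will be measured by two between-arm comparisons: the perioperative opioid total and the total after discharge. It gives no end to the second period. The same section says the device's effect will outlast the hospital stay, describes the time after discharge as one when many patients resort to opioids, and lists length of stay as another compared outcome.
- **Schedule.** Data Collection and Outcome Measures says: "The patient will be assessed 12, 24, 48, 72, 96 and 120 hours post-operatively to collect total opioid consumption". It expects some patients to go home before the last of these times: "For patients discharged with the device attached, removal instructions and pre-paid return envelope will be given to patient". The only contact after 120 hours is at 3 months. Its stated content is satisfaction with pain management and functional recovery; opioid use is not listed.

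**The concern.** An aim and a named efficacy measure depend on data that the schedule does not collect. If the protocol is followed as written, the after-discharge comparison is impossible for patients who stay 120 hours or longer. For the others it covers a short period whose length is set by the day they went home. Two patients with the same rate of use at home would then have different recorded totals because they left on different days. If the arms differ in length of stay, part of any difference in this total would come from the unequal periods.

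The pilot's data are meant to support a proposal for a larger trial. An after-discharge result missing for some patients, and covering unequal periods for the rest, would be of little use for that purpose.

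**Working it through.** The protocol states no figure on this point to reproduce. The check sets the promise beside the schedule and then works out the observed period.

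**Step 1: promise against collection**

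| Item | Period implied | Opioid collection described |
|---|---|---|
| Primary endpoint and Aim 1 | Around and after surgery | 12, 24, 48, 72, 96 and 120 h |
| Aim 3 and the second efficacy measure | From discharge, end not stated | Only what falls before 120 h |
| 3-month contact | Up to 3 months | None: satisfaction and functional recovery only |

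**Step 2: observed after-discharge period**

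Let *d* be the time of discharge in hours after surgery. With the last opioid assessment at 120 h, the observed period is max(0, 120 − *d*). This grants that the scheduled assessments continue at home.

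The protocol gives no length of stay, so these discharge times are assumed for illustration:

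- *d* = 48 h: 120 − 48 = 72 h
- *d* = 72 h: 120 − 72 = 48 h
- *d* = 96 h: 120 − 96 = 24 h
- *d* ≥ 120 h: 0 h

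**Step 3: dependence on length of stay**

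At a constant hourly use *u* at home, the recorded after-discharge total is *u* × (120 − *d*). Discharge at 72 h gives 48*u* and discharge at 96 h gives 24*u*. The ratio is 48/24 = 2, although use at home is the same. If stays are distributed alike in both arms, this mechanism creates no difference between arms. If they differ, the arm with the shorter stay records more after-discharge use at the same rate.

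**Step 4: comparison with the 3-month contact**

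If the intended period ran to 3 months (taken as 90 days, or 90 × 24 = 2160 h; an assumption, since no end is stated), the share observed would be:

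- *d* = 48 h: 72 / (2160 − 48) = 3.4%
- *d* = 72 h: 48 / (2160 − 72) = 2.3%
- *d* = 96 h: 24 / (2160 − 96) = 1.2%
- *d* ≥ 120 h: 0%

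**The case against.** The best defence has three parts.

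1. **Detail may sit elsewhere.** A statistical analysis plan may exist and may define each period. That answers questions of definition. It does not answer this one, because an analysis plan cannot create data that the schedule did not collect. The 3-month questionnaire might in practice include an opioid item, but the protocol does not say so.
2. **The assessments are not limited to inpatients.** The schedule says the patient will be assessed at all six times, and the same paragraph foresees patients at home with the device. On a plain reading, home use up to 120 h is meant to be collected and only the mode of contact is unstated. This stands, and Step 2 grants it. It leaves the period after 120 h uncovered.
3. **This is the third aim of a 60-patient pilot, not its primary endpoint.** This also stands and limits the weight of the point. The after-discharge total is nevertheless one of only two totals by which the protocol says efficacy will be measured.

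A reader might go further and infer that the primary endpoint itself has no usable period, or that its total will be biased because home doses go unrecorded. The document does not support either inference. The opioid schedule ends at 120 h, which matches "wearing a percutaneous, auricular field stimulator for five days" (5 × 24 = 120), and no competing period is stated, so 0 to 120 h is the natural reading. The exact period is also commonly left to an analysis plan. No sentence says that home doses will be left out, and any estimate of bias would rest wholly on assumed stays and assumed non-recording. Nor is it a contradiction that a home dose before 120 h could enter both totals, since nothing says they exclude each other.

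**Conclusion.** The point holds for the after-discharge comparison. Aim 3 and the second efficacy measure cannot be answered from the described schedule for any patient discharged at or after 120 h. For earlier discharges they can be answered only up to 120 h, over a period that shrinks hour for hour as the stay lengthens. This follows from the text alone and assumes only that the schedule is carried out as written.

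The number affected out of 60 cannot be derived, because no length of stay is given. The protocol expects some patients to leave before 120 h but does not say how many. Whether the unequal periods would distort the comparison between arms is likewise unknown: with equal stays they would not.

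The fault should be fixed before enrolment, since it cannot be repaired afterwards at the analysis stage. It does not undermine the primary endpoint, for which a clarification is enough.

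**What to change.** Choose one of two changes.

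- **Collect the data.** In Data Collection and Outcome Measures, add opioid use since discharge to the existing 3-month contact: whether the patient still takes opioids, and the amount taken or prescriptions filled. State the period covered, and use the same period in Aim 3 and in Pre-and-Post Metric Evaluation.
- **Narrow the claim.** Restrict Aim 3 and the second efficacy measure to discharge through 120 h, and state that patients discharged at or after 120 h do not contribute.

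The first is preferable because it lets the trial answer its own aim.

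As a brief clarification, state that the remaining opioid assessments (72, 96 and 120 h, as applicable) continue after discharge by call or diary, and that these home doses count in the 0 to 120 h primary total.

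The cost is some protocol wording, a short addition to a contact already planned, and a few short calls: three for a patient discharged just after the 48 h assessment, two after 72 h, one after 96 h. The grant already "will support a research coordinator in the execution of a pilot study", so the staff are in place. The drawback is recall error, largest at 3 months, and some diaries not returned.

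### The protocol answers dislike of the device only with leaving the study, and nowhere separates stopping the device from stopping follow-up

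*Protocol*

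**What the plan says.** Recruitment describes the intervention to patients as "wearing a percutaneous, auricular field stimulator for five days as a supplementary method of post-operative pain control". Data Collection and Outcome Measures then gives one answer for those who dislike the device: "they can drop out of the study at any time if they do not like wearing the" device. As to when this message is given, the same sentence reads "the patient will be made aware at the time of consent and throughout the trial". It is therefore repeated after randomization, while the device is being worn.

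The only removal described is the scheduled one for patients who go home wearing the device: "removal instructions and pre-paid return envelope will be given to patient to remove the device at 120 hours". Early removal, and what is collected after it, are not mentioned.

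The same section sets the assessments: "The patient will be assessed 12, 24, 48, 72, 96 and 120 hours post-operatively to collect total opioid consumption", and later "The patient will be contacted 3 months post-operatively to again assess patient satisfaction" and functional recovery. Neither sentence is made conditional on wearing the device, and neither says that the assessments continue once the device is off.

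On endpoints, Project Aims/Goals states: "The primary endpoint for this pilot study will be overall opioid consumption". Pre-and-Post Metric Evaluation measures efficacy by total perioperative consumption and also by "total opioid consumption after discharge between the two groups". Treatment Groups gives the control arm an inactive placebo device and the intervention arm an active one.

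**The concern.** The primary endpoint accumulates over time. A patient who leaves early contributes a partial total or none, and no later analysis plan can recover what was not collected. That is why the matter belongs in the protocol and the consent form: it concerns what patients are told and what is recorded, not how missing values are handled.

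The stated reason for leaving is a reaction to the device itself, which delivers stimulation in one arm only. The rate of leaving, or its relation to opioid need, could therefore differ between arms, and a comparison of those who remain would no longer be the comparison that was randomized. With 30 patients per arm, a 20% loss is six patients. The result is intended to support a larger grant application, so a distortion would carry forward.

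**Working it through.** **Reading the text.** Three statements stand side by side in Data Collection and Outcome Measures.

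1. Dislike of the device is met with dropping out of the study. No other option is stated.
2. Removal is described only at 120 hours.
3. Assessments to 120 hours and at 3 months are set for the patient in general.

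Statement 3 leaves room for follow-up after the device is off. Statement 1, in ordinary use, closes it. Nothing reconciles them for the patient who wants the device off but would accept further data collection.

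**Is there a plan figure to reproduce?** No. The 60 patients (30 per arm) are not presented as the result of a calculation, and no SD, dropout rate or dropout allowance is given. The only usable figures are the control mean of 100 mg IV morphine equivalent and the expected reduction of 50-70%.

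**Illustration, completers only.** Assumed: lognormal consumption with mean 100 mg and SD/mean 0.7. Dropout is logistic in log consumption; the gradient is the rise in log-odds of dropout per SD of log consumption, and the intercept is solved to give each dropout rate. The completer mean is E[Y(1 − p(Y))] / E[1 − p(Y)], by numerical integration. With no true effect, active versus placebo:

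| Dropout, active / placebo | Gradient, active / placebo | Completer means (mg) | Apparent effect |
|---|---|---|---|
| 20% / 5% | 0 / 0 | 100 / 100 | 0% |
| 20% / 5% | 0.5 / 0.5 | 93.4 / 98.2 | −4.9% |
| 20% / 5% | 1 / 1 | 87.5 / 96.2 | −9.0% |
| 5% / 20% | 1 / 1 | 96.2 / 87.5 | +9.9% |
| 12.5% / 12.5% | 1 / 1 | 91.5 / 91.5 | 0% |
| 12.5% / 12.5% | 0 / 1 | 100 / 91.5 | +9.3% |
| 12.5% / 12.5% | 1 / 0 | 91.5 / 100 | −8.5% |
| 20% / 5% | 0 / 1 | 100 / 96.2 | +4.0% |

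Equal rates do not guarantee an unbiased comparison. More dropout in the active arm need not favour the device (last row).

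**What a true 50% reduction would look like.** Halve the active completer mean. Gradient 1 in both arms:

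| SD/mean | Completer mean at 20% and 5% dropout (mg) | 20% active, 5% placebo | 5% active, 20% placebo |
|---|---|---|---|
| 0.5 | 90.9 and 97.3 | 1 − 0.5 × 90.9/97.3 = 53.3% | 1 − 0.5 × 97.3/90.9 = 46.5% |
| 0.7 | 87.5 and 96.2 | 54.5% | 45.0% |
| 1.0 | 82.9 and 94.5 | 56.1% | 43.0% |

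Over SD/mean 0.5 to 1.0 the reported reduction runs from about 43% to 56%.

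**If totals accrued up to leaving were analysed instead.** Unequal rates alone then suffice, even when leaving is unrelated to need. With 20% of the opioid used before leaving: 0.80 × 100 + 0.20 × 20 = 84.0 against 0.95 × 100 + 0.05 × 20 = 96.0, or −12.5% (+14.3% with the rates swapped). With 70% used: 94.0 against 98.5, or −4.6% (+4.8% swapped). The protocol does not say which analysis would be used.

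**The case against.** The strongest reply is that this argues from silence. The sentence can be read as no more than the ordinary right to withdraw: it does not say that data collection stops, that early removal counts as withdrawal, or that such patients are excluded. The assessments are not tied to wearing the device. The wording about patients discharged with it attached implies that some go home without it, yet the 3-month contact covers everyone. The consent form, where terms for continued data collection often stand, is not shown. Inpatient opioids are ordered in the surgeon's care plan (Appendix 2), so a record would ordinarily exist.

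Much of this stands. That dropping out ends data collection is an inference, and in-hospital totals may be recoverable. It does not remove the ambiguity: the protocol does not say that records will be used after a patient leaves, and inpatient orders do not capture use after discharge.

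The second reply is that the size is all assumption. That also stands. The documents give no dropout rate or SD and do not say whether patients can feel the stimulation. At SD 70 mg the standard error of the difference with 30 per arm is 70 × √(2/30) ≈ 18 mg, against non-zero completer shifts of about 4 to 9 mg in the first table.

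A reader might infer two stronger things: that the protocol requires follow-up to end when the device comes off, or that the comparison is biased in favour of the device. The documents support neither. No sentence orders follow-up to stop. Differential loss is plausible from the active versus inactive design but not shown, and the illustrations run both ways and include zero.

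**Conclusion.** The point holds as a clarification that should be made, with medium confidence. The protocol gives leaving the study as the only answer to disliking the device and provides no route to stop the device and stay in follow-up. Followed in its ordinary sense, it can cost part of the primary endpoint and, more readily, the post-discharge and 3-month data.

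The resulting bias is a risk whose size and direction cannot be determined. It is nil when leaving is unrelated to opioid need and only completers are analysed. The 43% to 56% range for a true 50% reduction rests wholly on assumed dropout rates, dependence on need, distribution and SD. It is modest against the expected 50-70% reduction.

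**What to change.** Replace the sentence in Data Collection and Outcome Measures, and align the consent form, with wording such as:

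> Patients may withdraw from the study at any time. Stopping use of the device, for whatever reason, is not in itself withdrawal from the study. Opioid consumption and adverse events continue to be collected at the scheduled times to 120 hours, and the post-discharge and 3-month assessments continue, unless the patient withdraws consent for data collection. The time of and reason for stopping are recorded and reported by arm.

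If continued follow-up is already intended, or already stands in the consent form, the protocol only needs to say so. The right to withdraw is unchanged, and no rule on when the device is removed is proposed.

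The cost is one protocol sentence and a matching consent line, using assessment times already scheduled. There is some follow-up effort for patients no longer wearing the device; the part after discharge cannot be costed because the protocol does not name the source of the opioid data. The effect estimate will be slightly diluted, because these patients stay in the comparison.

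### Aim 3 covers functional recovery, but function is assessed only at 3 months; adding the same measure before surgery would gain precision and let recovery be described

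*Protocol*

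**What the plan says.** Under Specific Aims, the third aim is to study the device's role in "reducing opioid consumption after discharge and facilitating functional recovery".

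Data Collection and Outcome Measures sets out what is recorded and when:

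- **Before surgery:** "demographic information and medical history will be collected from each participant on the day of surgery". No functional measure is mentioned.
- **12 to 120 hours:** patients are assessed "to collect total opioid consumption, incidence of adverse events, and level of comfort while wearing the NSS-2 BRIDGE device". Function is not on this list.
- **Discharge:** a satisfaction survey.
- **3 months:** the patient is "contacted 3 months post-operatively to again assess patient satisfaction with the pain management after surgery, and to assess functional recovery". No instrument is named.

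Pre-and-Post Metric Evaluation names opioid consumption, perioperative and after discharge, as the measure of efficacy. It then adds: "Other outcome measures include the incidence of respiratory depression, PONV, constipation and length of stay between the intervention and control groups". It lists no functional metric before or after surgery.

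Project Aims/Goals gives 30 active and 30 placebo devices and states: "The primary endpoint for this pilot study will be overall opioid consumption". Under Randomization Process, patients are "randomized by computer generated random numbers to either the control or intervention group", with no stratification stated.

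**The concern.** Recovery ordinarily means return towards the patient's own earlier level. One score at 3 months gives status at 3 months. A patient who was already limited before debulking and a patient made worse by surgery can have the same score. The inclusion and exclusion criteria set no functional-status requirement, so preoperative function may well vary.

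The timing of data collection is fixed in the protocol. A statistical analysis plan can choose a model, but it cannot adjust for a baseline that was never recorded, and once surgery has taken place that baseline cannot be collected prospectively.

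Two things are at stake. The first is the precision of the functional comparison in a small trial. The second is what the pilot can pass on: Pre-and-Post Metric Evaluation says its data will support a proposal for a full-scale trial, and without baseline scores it cannot supply the correlation between baseline and follow-up function that planning for this outcome would use.

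**Working it through.** **Stated figure.** The 60 participants appear as a device count. No SD, significance level or power is given, and there is no calculation for functional recovery, so there is nothing to reproduce.

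**Inputs.** From the protocol: n = 30 per arm. Assumed: two-sided 5% level, 80% power, all 60 assessed at 3 months, and a correlation r between baseline and 3-month function of 0.3 to 0.7. Results are in units of the SD of the 3-month score, by normal approximation.

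**Step 1, no baseline.**

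- Standard error of the arm difference: sqrt(2/30) = 0.258 SD.
- 95% confidence interval half-width: 1.96 × 0.258 = 0.51 SD.
- Detectable difference: (1.960 + 0.842) × 0.258 = 0.72 SD. A t-based calculation gives about 0.74 SD.

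**Step 2, with baseline adjustment.** ANCOVA multiplies the variance by 1 − r². The half-width and the detectable difference are multiplied by sqrt(1 − r²), and the equivalent unadjusted sample size is 30/(1 − r²).

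| r | 1 − r² | CI half-width (SD) | Detectable at 80% (SD) | Power for 0.5 SD | Equivalent n per arm |
|---|---|---|---|---|---|
| no baseline | 1.00 | 0.51 | 0.72 | 49% | 30 |
| 0.3 | 0.91 | 0.48 | 0.69 | 53% | 33 |
| 0.5 | 0.75 | 0.44 | 0.63 | 61% | 40 |
| 0.7 | 0.51 | 0.36 | 0.52 | 77% | 59 |

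The interval is shorter by about 5%, 13% and 29% respectively. Starting from the t-based 0.74 SD, the three detectable differences are about 0.70, 0.64 and 0.53 SD. The 0.5 SD used for power is illustrative, since the protocol gives no expected effect on function.

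**Step 3, incomplete follow-up.** If only 24 per arm were reached at 3 months (an assumption), the detectable difference would be 0.81 SD without a baseline and 0.77, 0.70 or 0.58 SD with one at r = 0.3, 0.5 or 0.7.

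**Step 4, chance imbalance.** The arm difference in baseline function also has standard error 0.258 SD. The probability of an imbalance above 0.25 SD is about 33%, and above 0.5 SD about 5%. An imbalance of 0.5 SD moves the 3-month difference by r × 0.5, which is 0.15 to 0.35 SD over this range. The unadjusted standard error in Step 1 already contains this variation, so it is the same loss as in Step 2 and must not be counted twice.

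**Step 5, change scores.** With equal SDs at the two times, the variance of a change score relative to the 3-month score is 2(1 − r): 1.4 at r = 0.3, 1.0 at 0.5 and 0.6 at 0.7. ANCOVA gives 0.91, 0.75 and 0.51. Analysing change gains nothing at r = 0.5, is noisier than the 3-month score below that, and is less precise than ANCOVA at all three values.

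**The case against.** **Bias.** A reader might infer that, without a baseline, the trial cannot tell an effect on recovery from differences in prior function. The protocol does not support that. Aim 3 in a randomised placebo-controlled trial is a question about the difference between arms. Randomisation balances prior function in expectation, so the expected arm difference in change equals the expected arm difference in the 3-month score. The planned comparison is unbiased. This part of the objection stands in full.

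**The instrument.** The protocol does not name one. A question about return to usual activities would carry its own preoperative reference, and recovery could then be described without a baseline score. This stands as a qualification. Such a question depends on recall at 3 months, and the protocol does not commit to one.

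**Silence is not exclusion.** The document is a short funding request and does not itemise the medical history. That is fair, but no functional measure is stated in any of its lists.

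**Size.** The gain depends on an assumed correlation and is small at 0.3. Even at 0.5, power for a 0.5 SD effect is only about 61%, so adjustment would not make this a confirmatory endpoint. A reader might also infer that chance imbalance could rival the treatment effect. The protocol states no plausible effect on function to compare it with.

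**Importance.** Opioid consumption is primary, and it is the endpoint that Project Aims/Goals ties to the NIDA proposal. Functional recovery is half of a third aim. This limits the weight of the point but does not remove it.

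**Conclusion.** The point holds as a gap in data collection that limits precision and description. Function is assessed once, at 3 months, with no stated preoperative measure, and no later analysis plan could repair that. Without a baseline, the detectable difference at 30 per arm is about 0.72 to 0.74 SD, depending on the approximation. On the normal approximation, adjustment lowers it to about 0.69 SD (r = 0.3), 0.63 SD (r = 0.5) or 0.52 SD (r = 0.7).

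These figures assume complete 3-month follow-up, a roughly continuous score and the stated range of r. If the instrument chosen asks about return to usual function, the loss in describing recovery largely falls away and the case rests on precision.

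The planned comparison is not biased. This is a worthwhile, inexpensive improvement to a secondary aim of a pilot.

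**What to change.** Name the function measure to be used at 3 months, and give the same measure once before surgery, either at consent in the pre-surgical clinic or with the day-of-surgery data. Compare the arms on the 3-month score by ANCOVA adjusted for the baseline score. Report change from baseline by arm descriptively only.

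The cost is one short questionnaire at a contact that already takes place, handled by the research coordinator whom the grant is to support. It needs no extra visit and adds one covariate to the analysis. The downside is a few minutes of patient burden before surgery.
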